	
9. Cohort 2 comprises therapy refractory subjects:
 
 
a Subject did not achieve immunological remission after prior IST(s) as documented by the investigator AND
 
b Subject is without promising standard therapeutic options as documented by the investigator (i.e. investigator expects efficacy or safety issues with remaining IST options) AND
 
c Serum anti-PLA2R antibodies <math>\geq 20.0</math> RU/mL measured at screening by the Euroimmun ELISA at central laboratory.
 
 
Note: France will only enroll patients in Cohort 2.
 
Parameters in italics are measured in a central laboratory.

Key Exclusion Criteria	
 
1. Hemoglobin <math>< 80</math> g/L.f
 
2. Thrombocytopenia: Platelets <math>< 100.0 \times 10^9/L</math>. *
 
3. Neutropenia: Neutrophils <math>< 1.5 \times 10^9/L</math>.#
 
4. Leukopenia: Leukocytes <math>< 3.0 \times 10^9/L</math>.#
 
5. Hypogammaglobulinemia: Serum immunoglobulins <math>\leq 4.0</math> g/L.f 
 
f Subjects may receive blood transfusions or erythropoietin to meet the criterion.
 
* Subjects may receive thrombopoietin to meet the criterion.
 
# Subjects may receive colony stimulating factors to meet the criterion.
 
‡ Subjects may receive immunoglobulin substitution to meet the criterion.
 
 
 
6. B-cells <math>< 5 \times 10^6/L</math>.
 
7. Secondary cause of MN (e.g. systemic lupus erythematosus (SLE), medications, malignancies) as determined by the investigator.
 
8. Concomitant renal disease other than MN (e.g., diabetic renal disease, lupus nephritis, IgA nephropathy).
 

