## 7.2. Exclusion Criteria

Since deviations from exclusion criteria can have a negative impact on subject safety or the scientific integrity and regulatory acceptability of the clinical trial, the sponsor will not provide waivers to them. Subjects must be excluded from participating in this clinical trial if they meet any of the following criteria at screening (*parameters in italics will be tested at screening; parameters not in italics will be determined locally*):

1. *Hemoglobin*  $\leq 80$  g/L‡
2. *Thrombocytopenia: Platelets*  $\leq 100.0 \times 10^9/L^*$
3. *Neutropenia: Neutrophils*  $\leq 1.5 \times 10^9/L^\#$
4. *Leukopenia: Leukocytes*  $\leq 3.0 \times 10^9/L^\#$
5. *Hypogammaglobulinemia defined as serum immunoglobulin*  $\leq 4.0$  g/L‡
  - f Subjects may receive blood transfusions or erythropoietin to meet the criterion.
  - \* Subjects may receive thrombopoietin to meet the criterion.
  - # Subjects may receive colony stimulating factors to meet the criterion.
  - ‡ Subjects may receive immunoglobulin substitution to meet the criterion.
6. *B-cells*  $\leq 5 \times 10^8/L$ .
7. Secondary cause of MN (e.g. SLE, medications, malignancies) as determined by the investigator.
8. Concomitant renal disease other than MN (e.g., diabetic renal disease, lupus nephritis, IgA nephropathy).

CCI

CCI

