### 8.3. Concomitant Therapy

Subjects are allowed to continue medications that they are taking at baseline, particularly, supportive therapy for MN and therapy initiated at screening such as immunoglobulin substitution or erythropoiesis stimulating agent (ESA) therapy. Subjects are allowed to receive concomitant medications that are medically indicated as standard of care for the treatment of symptoms and intercurrent illnesses, unless they fall under prohibited medications. Subjects may also receive therapy to mitigate side effects of the trial medication as clinically indicated, as well as best supportive care as per institutional guidelines. This may include medications such as diuretics, anti-lipid-medication, anti-hypertensive (e.g. ACEI), anticoagulation, antiemetics, antidiarrheals, anticholinergics, antispasmodics, antipyretics, antihistamines, analgesics, or antibiotics. The Investigator should instruct the subject not to take any additional medications (including over-the-counter products) during the trial without prior consultation.

Investigators should document all medication and other therapy (including non-drug procedure) taken by/administered to the subject during the entire course of the trial including the screening and the follow-up phase. The entry must include the dose, regimen, route of administration, indication, and dates of use (start, end).

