### 8.3.2 Infection Prophylaxis

The immunoglobulin level will be monitored throughout the trial. If this level drops below 4 g/L, initiating substitution therapy with a polyvalent immunoglobulin according to local institutional guidelines is advised. Generally, a trough level of at least 5 g/L shall be targeted, with a substitution of 0.2 g per kg body weight every 3 to 4 weeks.

Furthermore, investigators may follow institutional guidelines on infection prophylaxis for subjects regarded to be at high risk of infection.

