## 10.1. Screening Phase

All subjects must meet all inclusion criteria and none of the exclusion criteria listed in [Section 7.1](#) and [Section 7.2](#). Signed and dated informed consent must be obtained from all subjects prior to their entering the clinical trial.

The Screening Phase begins on the date when the ICF is signed; it will last for up to 42 days and is followed by treatment start (Cycle 1 Day 1, C1D1).

The assessments to be performed at screening are:

Documentation of

- Informed consent
- Medical history including results of biopsies and disease therapy history
- Laboratory values including
  - o proteinuria
  - o all available historic anti-PLA2R titers and IFT results
- Demography (age, gender, race)
- Prior and concomitant medications
- Allergies and hypersensitivities

Assessment of

- In- and exclusion criteria
- Physical examination
- Electrocardiogram (ECG)
- Vital signs (blood pressure, heart rate, body temperature)
- Weight (in kg without decimals with 1st decimal rounding in case of higher precision scales; e.g. 67.4 rounded to 67; 67.5 rounded up to 68)
- Height (in centimeter without decimals)

Laboratory

- Complete blood count with differential white blood cell count (CBC)
- B-cell count
- HbA1c
- Serum biochemistry including immunoglobulins

- Hepatitis B/C, HIV Serology/Virology (incl. PCR confirmation)
- Lipid panel
- Urine analysis
- eGFR
- Liver function tests (AST, ALT, gamma-GT, bilirubin)
- 24 hour urine for urine protein, creatinine, and sodium

An abnormal laboratory value may be reanalyzed during the screening phase.

Substitution with immunoglobulins before or during screening is permitted. Data on immunoglobulin administration should be entered in the eCRF as concomitant medication.

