## 7.7. Baseline

Baseline is the result of an investigation describing the “true” uninfluenced state of the subject, defined as the period from the date of signing any informed consent document to the start date of study drug.

Unless otherwise stated in the respective sections, the last non-missing assessment, including unscheduled assessments, on or before the start date of study drug prior to the first dosing of the study drug will be used as “baseline” value or “baseline” assessment. Assessments collected post-dose on the first date of treatment are not considered as baseline values.

Baseline values for proteinuria responses are defined in the respective section.

If a subject has no value as defined above, the baseline value will be considered as missing.

Data listings will include baseline flags.

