#### Laboratory Tables

- Central haematology, coagulation and serum biochemistry parameters
  - Descriptive summaries of absolute values and absolute change from baseline values will be presented for continuous parameters for FAS by visit
  - Number (%) of subjects at each time point having clinical relevant findings of laboratory parameters will be tabulated by visit for each clinical laboratory parameter
  - For each laboratory parameter shifts in assessments from baseline (low, normal or high) to worst-post baseline will be presented based on classifications relative to the laboratory reference ranges (low/normal/high) for laboratory parameters where NCI-CTCAE grades are not defined. If a subject experiences both "low" and "high" assessments in the course of the trial, the worst post-baseline will be defined as "Low and High"
  - If NCI-CTCAE grades are available for a clinical laboratory parameter, frequency and shift tables based on grades will be created as follows:
    - Number (%) of subjects with worst post-baseline grade. Each subject will be counted only for the worst grade observed on-treatment.
    - Shift tables to compare baseline to the worst post-baseline value using CTCAE grades for laboratory parameters where grades are defined
- Central serology parameters
  - Descriptive summaries of absolute values and change from baseline values will be presented for FAS by visit
- Cytokine (due to IRR  $\geq$  grade 3)
  - Descriptive summaries of absolute values will be presented for FAS on visits where the IRR was observed (split by samples taken at time of IRR and 24 hours after IRR)
  - Absolute and relative change from baseline, if the baseline values are available
- 24 hour urine
  - Analysis of parameters from 24h urine is described in section 10.2
- Spot Urine
  - Descriptive summaries of absolute values and change from baseline values for UPCR from spot urine will be presented for FAS by visit

The tables will include only assessment on-treatment.

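### By-visit immunoglobulin and haemoglobin summaries mix values taken under supportive therapy with unsupported values, so the mean changes are confounded, in either direction

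*SAP*

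**What the plan says.** **Support before baseline.** Protocol section 7.2 allows support to get past the laboratory exclusion criteria. For haemoglobin: "Subjects may receive blood transfusions or erythropoietin to meet the criterion". Similar notes cover thrombopoietin, colony-stimulating factors and immunoglobulin. Section 10.1 adds: "Substitution with immunoglobulins before or during screening is permitted".

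**Support on study.** Section 8.3 lets subjects continue "therapy initiated at screening such as immunoglobulin substitution or erythropoiesis stimulating agent (ESA) therapy". Section 8.3.2 advises starting immunoglobulin when the level is under 4 g/L: "Generally, a trough level of at least 5 g/L shall be targeted", with substitution every 3 to 4 weeks. Section 10.1 foresees red-cell transfusion during treatment, in its guidance on blood-bank interference.

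**Baseline.** SAP section 7.7 presents baseline as the true "uninfluenced state of the subject, defined as the period from the date of signing any informed consent document" up to the start of study drug. In practice it takes the latest available pre-dose value, with no condition on support.

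**Tables.** Protocol Table 3 lists immunoglobulins under central serum biochemistry, so they fall under SAP section 11.6.3: "Descriptive summaries of absolute values and absolute change from baseline values will be presented for continuous parameters for FAS by visit". Neither the tables nor the laboratory listings carry a flag, split or sensitivity analysis for values under support. Concomitant medications are tabulated and listed separately (SAP section 9.7.3), without a link to the laboratory results.

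**The concern.** Protocol section 6.8 names depletion of plasma cells and plasmablasts as a major pharmacological effect of MOR202. It answers the resulting immune risk partly by monitoring, and where needed substituting, total serum immunoglobulin. Substitution is triggered by the outcome itself: the subjects whose levels fall furthest are the ones whose later values are raised. A by-visit mean that pools these values does not describe what the drug did to immunoglobulin. A baseline raised to reach eligibility has the opposite effect, because its decay is tabulated as a fall on treatment.

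The SAP accepts the general principle for efficacy. Start of prohibited treatment stops the counting of responses (section 7.13.3), and section 10.10 excludes subjects given relevant immunosuppressive therapy in a sensitivity analysis. The laboratory safety tables have no counterpart, although safety is the primary objective.

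**Working it through.** **Plan's own figures.** The only design calculations are the probabilities of seeing an adverse event at least once (protocol section 12.5). 1 − 0.90^20 = 0.878 (stated 88%) and 1 − 0.85^10 = 0.803 (stated 80%). Both reproduce, and the point does not depend on them.

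**Inputs from the protocol.** Immunoglobulin trigger below 4 g/L; target trough at least 5 g/L; interval 3 to 4 weeks (all section 8.3.2). About 20 subjects in Cohort 1 and 10 in Cohort 2.

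**Step 1: lift per substituted subject.** Target minus trigger is at least 5 − 4 = 1.0 g/L. This assumes that the target is reached and that the unsupported level would have stayed at or below the level that triggered support.

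**Step 2: effect on the mean change.** With k subjects newly substituted after baseline, attenuation is at least k × 1.0 / n.

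| k | n = 20 | n = 10 |
|---|---|---|
| 1 | 0.05 g/L | 0.10 g/L |
| 3 | 0.15 g/L | 0.30 g/L |
| 5 | 0.25 g/L | 0.50 g/L |

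The documents do not predict k, so the range is illustrative.

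**Step 3: direction.** Bias in mean change = (share supported at the visit − share supported at baseline) × lift. Single-subject examples in g/L, with assumed levels and a lift of 5.0 − 3.9 = 1.1:

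| Support | Unsupported change | Tabulated change | Bias |
|---|---|---|---|
| After baseline only (baseline 6.0, fall to 3.9, raised to 5.0) | −2.1 | −1.0 | +1.1 |
| At baseline only (3.9 raised to 5.0, drifts back to 3.9) | 0 | −1.1 | −1.1 |
| At both times (3.9 raised to 5.0 and held there) | 0 | 0 | 0 |

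In the third case the change is right, but the absolute values are too high.

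**Step 4: timing.** From Cycle 2, scheduled treatment visits are 28 days apart. If substitution follows the 3 to 4 week interval, nearly every later scheduled on-treatment value of a substituted subject is a supported one.

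**Step 5: size if substitution were common.** This is a simulation on assumed inputs that are not in the documents: log-normal baseline with the median shown and SD about 2 g/L, baselines of 4 g/L or less removed, an average proportional fall as shown, every later value under 4 set to 5, and no support at baseline.

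| Median baseline | Fall | Share below 4 g/L | True mean change | Tabulated | Attenuation |
|---|---|---|---|---|---|
| 7 g/L | 30% | 23% | −2.19 | −1.83 | 0.36 |
| 7 g/L | 50% | 66% | −3.67 | −2.40 | 1.27 |
| 6 g/L | 30% | 37% | −1.99 | −1.39 | 0.60 |
| 6 g/L | 50% | 77% | −3.34 | −1.73 | 1.61 |

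**Step 6: other outputs.** The worst-post-baseline tables keep a low value measured centrally on treatment before support began. Where no CTCAE grade exists, section 11.6.3 gives only low/normal/high shifts. A subject low at baseline then stays low-to-low at any depth, while a baseline raised into the normal range turns the same subject into a normal-to-low shift. By-visit summaries also leave out unscheduled values (SAP section 7.10).

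**Haemoglobin.** The protocol gives no haemoglobin target under support, so no figure is offered. The mechanism is the same.

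**The case against.** The strongest reply is that summarising values as observed is legitimate in an uncontrolled, descriptive trial, and that other outputs cover much of the ground. Immunoglobulins and blood counts are taken at every visit, so a drop under 4 g/L would ordinarily be caught and enter the worst-value tables. Clinically relevant abnormalities become adverse events (protocol section 10.8.1) and so feed the primary endpoint. Grade 3 or higher neutropenia and thrombocytopenia are events of special interest. Protocol section 12.12.1 promises discussion of events that needed significant additional therapy. A fall from 6.0 to 3.9 g/L is −35% and would exceed the 25% worsening limit of SAP section 11.2. All of this stands, and it limits the point to the by-visit means and, in part, to the shift tables.

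A reader might infer three stronger things that the documents do not support.

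- *That the tables always mask the drug's effect.* Step 3 shows that the bias can take either sign or vanish.
- *That all four kinds of support are plainly allowed on study.* Only immunoglobulin and ESA are named. Colony-stimulating factors and thrombopoietin rest on the general clauses of section 8.3, and section 8.4 bars biological response modifiers without saying whether growth factors belong to them. Needing platelet transfusion ends MOR202 treatment (section 8.8.1).
- *That the primary endpoint is distorted.* It is the incidence and severity of TEAEs, not a laboratory mean.

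The reply does not remove the gap. No planned table shows how many values at a visit were supported, and none counts low immunoglobulin and start of substitution together.

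**Conclusion.** The point holds for the by-visit immunoglobulin summaries and, by the same mechanism, for haemoglobin under transfusion or ESA. Support begun after baseline attenuates the mean fall by at least 0.05 g/L per substituted subject at n = 20 and 0.10 g/L at n = 10. This rests on the target trough being reached and on no recovery without support. Waning support from before baseline works the other way. The net effect cannot be known in advance, because the documents do not say how many subjects will be supported or when.

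The description of baseline as uninfluenced also conflicts with support given to reach eligibility. The affected outputs are supportive safety displays, so this is a gap worth closing in the SAP and not a flaw in the primary analysis.

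**What to change.** Amend SAP section 11.6.3, with a cross-reference in section 7.7. No clinical rule changes.

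1. **Baseline.** Keep the last pre-dose value, flag it as supported where applicable, and qualify the wording of section 7.7. Do not substitute the value from before support. Support may predate screening, so such a value may not exist. A subject raised from 3.9 to 5.0 g/L whose support continues would also show 5.0 − 3.9 = +1.1 g/L on MOR202.
2. **Later values.** Flag values taken under support in tables and listings, and give the number of supported subjects at each visit. Define under support in advance, for example within 28 days of immunoglobulin (the upper end of the protocol's interval), with a stated window for transfusion and ESA.
3. **Composite count.** By cohort, count subjects with immunoglobulin below 4 g/L or substitution started on treatment as one outcome. Add the analogous haemoglobin item: a value below a threshold already in the protocol (80 g/L in the eligibility criteria or 60 g/L in section 8.7; the SAP should name which), or transfusion or ESA started. Show subjects already supported at baseline separately. Later support cannot hide an event in this count.
4. **Summaries without supported values.** Show these only beside the full summary, with a note that the exclusion is informative. By Step 4, the subjects with the largest falls would lose most of their later values.

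The cost is SAP wording and a small amount of programming. Protocol sections 8.1, 8.3 and 10.1 already require these therapies to be recorded in the trial data, with doses and dates.

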## 6.5. Treatment Phase

All subjects enrolled in the trial will be treated for 24 weeks across six 28-day treatment cycles.

In total, 9 doses of MOR202 will be administered on the following treatment days: Cycle 1 Day 1, 8, 15 and 22, and on Day 1 of Cycle 2 to 6 (for details see [Figure 1](#) and [Table 2](#)).

The Treatment Phase ends with the EOT visit, scheduled between 28 and 42 days after the last administration of MOR202. For details see [Section 10.4](#).

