### **8.8.3. Discontinuation due to efficacy - stringent immunological complete remission**

Furthermore, treatment may be discontinued for subjects with stringent immunological complete remission (sICR) confirmed by repeat measurement at least 25 days apart. These subjects will follow their planned schedule, but will not be treated at the following CxDI visits, unless a subject turns positive again during the treatment phase.

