### **8.8.4. Withdrawal due to Subject Decision**

Each subject is free to withdraw from the clinical trial at any time. All efforts will be made to complete and report the observations up to the time of withdrawal as thoroughly as possible. A complete final evaluation at the time of the subject's withdrawal should be made (all assessments scheduled for EOT/EOS visit depending on time of withdrawal). An explanation why the subject

is withdrawing from the clinical trial should be provided. If withdrawn in the treatment phase, these subjects will not enter the follow-up phase.

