### **10.5. Follow-up Phase**

Safety measurements will be performed in the Follow-Up Phase which spans from the EOT Visit until the EOS Visit: **EOT takes place 28 days after the last administration of MOR202.** The visit window is + 14 days, thus up to 42 days after the last administration of MOR202. After the EOT visit subjects will be followed up for further 28 weeks at two visits with an interval of 14 weeks each: FUV and EOS. For assessments refer to the Schedule of Assessments (Table 2).

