### 7.3.2. Date of last administration of study drug

The date of last administration of study drug for a subject is the last date when a non-zero dose of study drug is administered and is referred to as “end date of study drug”.

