## 7.8. On treatment assessment/event

### On-treatment assessment/event

An on-treatment assessment/event is defined as any assessment/event happening after the start date of study treatment, i.e. assessments/events happening in the following time interval (including the lower and upper limits):

[Start date of study drug +1 day; End date of study drug + 28 days].

Assessments collected post-dose on the start date of study drug are also considered as on-treatment assessments. Data listings will include all assessments/events, flagging those which are not on-treatment assessments/events.

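### SAP 11.6.3 laboratory tables stop 28 days after the last dose, so a protocol-compliant late EOT sample and the follow-up blood counts, immunoglobulins and most chemistry are listed but not summarised there

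*SAP*

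**What the plan says.** SAP 11.6.3 specifies by-visit summaries, worst-grade counts and shift tables for central haematology, coagulation and serum biochemistry (immunoglobulins belong to biochemistry in Protocol Table 3), and summaries of spot-urine UPCR. It closes the list with "The tables will include only assessment on-treatment". The worst-grade rule repeats the limit: "Each subject will be counted only for the worst grade observed on-treatment".

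SAP 7.8 defines on-treatment as "Start date of study drug +1 day; End date of study drug + 28 days", plus post-dose assessments on the first day. Everything later is post-treatment. SAP 7.3.2 fixes the end date as "the last date when a non-zero dose of study drug is administered".

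The protocol sets a different clock for the visit itself. Section 6.5: "The Treatment Phase ends with the EOT visit, scheduled between 28 and 42 days after the last administration of MOR202". Section 10.5 repeats the upper limit: "thus up to 42 days after the last administration of MOR202". Protocol Table 2 schedules CBC, serum biochemistry and immunoglobulins at EOT, FUV and EOS.

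Two other SAP texts pull the other way. Section 7.10 builds by-visit summaries on the nominal visit and ignores assessment windows. The reference-range shift rule inside 11.6.3 refers to low and high values over the whole trial, not over treatment.

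**The concern.** Whether a subject's EOT value appears in the EOT column depends on the appointment date. A sample on day 28 is in; one on day 29 is out, although the protocol accepts both. For a subject who completes dosing, EOT is the first scheduled blood count after the last dose, because the C6D1 bloods are drawn before dosing.

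FUV and EOS values never enter these tables. Safety is the primary objective and safety after treatment a secondary one. Protocol 6.8 names plasma-cell depletion as a major pharmacological effect, with immunoglobulin monitoring as one safeguard. Yet these tables cannot show whether immunoglobulins or counts recover. Laboratory data are treated differently from neighbouring safety data: SAP 11.3.2 summarises vital signs at every available time point, and SAP 11.1.4 gives AEs, SAEs and AESIs their own post-treatment tables.

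**Working it through.** **Inputs.** Nominal days from Protocol Table 2: C1D8 8, C1D15 15, C1D22 22, C2D1 29, C3D1 57, C4D1 85, C5D1 113, C6D1 141, EOT 169, FUV 267, EOS 366. A visit is tabulated if its day ≤ day of last dose + 28 (SAP 7.8).

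**1. The protocol's own EOT window.** 169 − 141 = 28 days; 28 + 14 = 42 days. This reproduces the stated 28 to 42.

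**2. Overlap with on-treatment.** Days 28 to 42 are 42 − 28 + 1 = 15 allowed days. Only day 28 is on-treatment; the other 14 are not.

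**3. Follow-up visits.** FUV: 267 − 141 = 126 days after the last dose (112 to 140 with the ±14-day window). EOS: 366 − 141 = 225 days (211 to 239). Both always exceed 28.

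**4. Scheduled post-baseline visits lost, last dose on Day 141 (cut-off Day 169).**

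| Parameter | Scheduled | Lost, EOT on day 28 | Lost, EOT on days 29–42 |
|---|---|---|---|
| CBC, chemistry, immunoglobulins | 11 | 2 (18%) | 3 (27%) |
| Coagulation (C1D15, C4D1, EOT) | 3 | 0 | 1 |
| Spot-urine UPCR (C4D1, C5D1, C6D1, EOT, FUV, EOS) | 6 | 2 | 3 |

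The spot-urine row matters little, because Protocol 3.2 defines proteinuria by 24-hour UPCR.

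**5. Subjects not dosed after confirmed sICR.** Protocol 8.8.3 requires the response to be "confirmed by repeat measurement at least 25 days apart" and keeps these subjects on their planned visits. On nominal days, C1D8 to C2D1 is 29 − 8 = 21 days, which is too short. C2D1 to C3D1 is 57 − 29 = 28, so C3D1 is the earliest confirming visit. Assume that the dose is given at the confirming visit, that dosing is not resumed, and that visits stay on the planned calendar:

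| Last dose | Cut-off day | CBC visits lost of 11 | If the visit due on day 28 is late | Planned EOT, days after last dose |
|---|---|---|---|---|
| C3D1 (57) | 85 | 5 | 6 | 169 − 57 = 112 |
| C4D1 (85) | 113 | 4 | 5 | 169 − 85 = 84 |
| C5D1 (113) | 141 | 3 | 4 | 169 − 113 = 56 |

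The last column conflicts with Protocol 6.5 and 10.5, which place EOT 28 to 42 days after the last administration, and with Protocol 10, which recalculates each visit from the previous administration. These passages must be reconciled. Until then the table is conditional on the planned-calendar reading.

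**6. Early EOT-type assessments.** After discontinuation under Protocol 8.8.1 or 8.8.2, EOT is again no earlier than 28 days after the last dose. A subject who withdraws by choice should have a final evaluation at that time ("all assessments scheduled for EOT/EOS visit depending on time of withdrawal"). It can fall within 28 days and is then tabulated, unless SAP 7.12.8 removes it as data collected after withdrawal of consent.

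**The case against.** The strongest reply is that nothing promised is broken. The follow-up safety objective has one endpoint, AE incidence and severity, and SAP 11.1.4 tabulates post-treatment AEs in full. The laboratory cut-off equals the end of the TEAE window. Protocol 12.12.3 promises listings of all data, and SAP 11.6.3 lists individual results by visit and out-of-range values with grades and flags. Under Protocol 12.12.2 the sponsor reviews each laboratory result for new abnormalities and worsening, with no on-treatment limit. Clinically relevant values become AEs (Protocol 10.8.1). Neutropenia and thrombocytopenia of grade 3 or higher are AESIs (Protocol 10.8.7) with post-treatment tables. With about 30 subjects, graded listings can be read by eye. All of this stands and limits the consequence.

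A second reply is that SAP 7.10 and the trial-wide shift rule could lead a programmer to keep a late EOT sample. That is possible. But neither text overrides the explicit closing restriction, and an ambiguity that lets two programmers produce different tables itself needs correcting.

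Third, the predose timing should not be overstated. Each predose value follows an earlier dose by 7 or 28 nominal days, so only the last dose lacks a tabulated follow-up value when EOT is late.

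A reader might infer that follow-up laboratory safety goes unreported, or that the secondary objective is not analysed. The documents do not support that, for the reasons above. Nor do they show that late immunoglobulins or counts are summarised nowhere. Protocol 12.11.4 carries immune-cell populations to EOS, SAP 10.2 summarises 24-hour urine to end of study, SAP 10.10 points to separate eGFR and albumin analyses, and SAP section 14 is largely redacted.

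**Conclusion.** The point holds as a reporting gap confined to SAP 11.6.3. On its explicit restriction, a compliant EOT sample after day 28 and all FUV and EOS values are left out of the by-visit, worst-grade and shift tables. For a completer's CBC, chemistry and immunoglobulins this is 2 of 11 scheduled post-baseline visits, or 3 of 11 if EOT is late. The values affected are late ones not reported as AEs, apart from albumin, eGFR and 24-hour urine, which are analysed elsewhere.

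The counts rest on nominal days and on the explicit restriction governing over SAP 7.10. The sICR figures also need the assumptions in step 5, and stopping for sICR is optional and reversible. The documents do not give the share of subjects with a late EOT or an sICR stop, so the number of subjects affected cannot be stated. A reader might take 14 of 15 allowed days to mean that most EOT samples are lost. That does not follow, since day 28 is the target and the distribution of visit dates is unknown.

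**What to change.** 1. In the 11.6.3 by-visit tables, summarise all scheduled visits through EOS by nominal visit, as SAP 7.10 does. A late EOT sample then stays in the EOT column.
2. Leave the on-treatment worst-grade and shift tables on the window ending at last dose + 28 days, in line with TEAEs. Add parallel post-treatment worst-grade and shift tables for CBC, chemistry and immunoglobulins from last dose + 29 days to EOS. These hold late EOT samples and the later values of subjects who stopped for sICR. Moving days 29 to 42 into the on-treatment tables would be wrong, because an AE starting on those days counts as post-treatment under SAP 11.1.
3. State which window the reference-range shift rule uses, and reconcile the protocol passages on EOT timing after an sICR stop.
4. Optional and separate: SAP 11.6.2 merges low and high CTCAE grades, so a same-grade change from low to high appears as no shift. Tabulate the two directions separately for parameters graded both ways.

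The cost is SAP wording and a few more tables from data already collected. Some laboratory toxicity counts may look less favourable.
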